### 10.3 Procedures for Assessing Variable:

#### 10.3.1 Limb dimensions and surface area:

The term 'limb' refers to the forearm and the lower leg. The surface area of each limb is computed as the average of four evenly spaced circumferences (two peripheral, two central) of the forearm (elbow to wrist) or lower leg (back of knee to ankle) multiplied by the length of treatment area. The locale along the limb at which each circumference is taken will be recorded (for later use in the study, see section 10.3.3, below) as the distance in centimeters from the distal margin of the site of the most distal circumference site (i.e., at wrist or ankle).

# 10.3.2 Familiarization with, and subject use, of each spray apparatus:

Variable assessment will involve a two-step process, namely subject familiarization with the spray apparati, followed by dosage measurement.

Subjects will practice application of test materials to their own limbs under the following procedure (next paragraph), which will be reviewed for the subjects by a researcher before practice commences. The copies used during the study will be formatted for greater clarity and ease of use than is possible here.

"Read along on your copy of the procedure as the Researcher reads them to you. Ask questions of the Researcher as they occur to you or at any time thereafter. Be sure to get answers to any questions you feel should be answered before proceeding at any step of this work.

This is a study of your behavior in applying spray insect repellents. You will probably have had experience with applying spray products of some kind to your skin before. If you are uncertain about how to use a spray dispenser be sure to ask the Researcher or one of the technicians. You will each have the opportunity to practice these procedures with the aid of a technician.

Insect repellents function to repel insects from biting the skin. Their effectiveness is influenced by the completeness of their application to the skin surface. Our goal is to determine your preferred method for achieving **full coverage**. At minimum, **full coverage** is defined as a continuous and complete layer of test material. Orienting the arm to light may aid in determining whether full coverage has been achieved. Spray as much as necessary to achieve full coverage.

In these instructions, the act of spraying a repellent on your arm will be termed 'spraying', 'application', or 'dispensing.'

If you are wearing a long-sleeved shirt roll the sleeves so as to expose the entire lower arm. Wash arms thoroughly with the provided cleanser and dry with a clean towel. Place new latex or vinyl gloves on each hand, choosing the size that fits you most snugly without being uncomfortably restricting or likely to tear when you put them on.

You will work with a technician who will assist you in measuring and recording your use of a repellent product in two delivery systems, a pump spray and an aerosol spray.

Work first with the pump spray, second with the aerosol spray. Because they are similar, the application instructions below describe the procedures for each type of spray together in each paragraph.

Familiarize yourself with the spray mechanism. Any actuation (pushing down on the pump plunger) of the spray must take place out-of-doors. Work at a distance of no less than 6 feet (1.9 meters) from other subjects. Do not dispense the spray at or near

your face or anyone else's. Minimize inhalation of airborne spray while working.

Testing will take place out-of-doors during daylight hours at an air temperature (shade) above 14 °C (57 °F) and wind speed below 12 kph (7 mph), with no precipitation. The researcher or a technician will inform you when these conditions are not met and spraying of the repellents will cease until those conditions resume.

Dispense the spray on one forearm, using the opposite hand. By successively moving the spray nozzle closer to and farther from the arm, identify a distance between nozzle and skin that seems most appropriate for effective application to the skin. The technician will measure and record that distance to the nearest centimeter on the provided datasheet.

Have the technician wash and dry the treated arm so that none of the repellent you have applied is visible on close inspection.

Now, using the spray nozzle at or near the distance from the skin that you have just chosen to be effective for application, determine the minimum number of actuations (pumps of the pump spray) or longitudinal passes (aerosol) required to give full coverage of all surfaces of the forearm. For the pump spray, depress the plunger fully each time, and count them aloud beginning with "1, 2, 3 ...." etc. If you partially depress the plunger (rather than fully depress it) in order, e.g., to apply to a small skin area not covered be initial application, report that to the technician as a "half pump." Each partial depression should be so reported as it occurs. If on any given actuation material fails to be delivered, do not count that actuation. If a partial amount is delivered, consider it either 'whole', 'half' or 'none' and report it as such. For 'none', simply resume counting at the next actuation that delivers material to the skin.

Report the count to the technician who will record it on the data sheet. The technician will also assist you in keeping track of whole versus half pumps.

When applying the aerosol, announce each onset of spraying with the word "START" and each cessation with the word "STOP". This will aid the technician who is counting your application time. Apply the aerosol in a series of full "sweeps" (passes) between the wrist and elbow. There may be more than one start and stop while working to achieve full coverage of the arm. Count each one-way sweep as one sweep, and count passes in a manner analogous to that used for pump spray (above). If you make a partial sweep that you judge to be closer to a "half sweep" than a "full sweep", call it out to the technician as a "half". Treat accidental under-applications in the same manner as for the pump spray (described above). Try not to let your awareness of the technician's timing to influence you dispensing behavior. If the technique of using mainly full sweeps seems awkward or unnatural to you, inform the technician immediately. Your preferred method should be demonstrated for the Researcher, who will determine how it may be quantified.

Repeat the application procedure and collect the same data for the other arm.

Discard your latex gloves, and wash both arms with cleanser and dry them thoroughly with a towel.

Put on new gloves, and repeat the application procedure twice more (both arms) with the pump spray. During these two repetitions the technician will again measure your preferred distance between the nozzle and the skin, and quantify the application as before. However, in these repetitions, if you are confident that you have learned and remembered your preferred distance, you and the technician can measure the distance you used *after* reporting the data on number spray pumps/number and duration of aerosol sweeps. This will avoid interrupting your application with additional arm washing by the technician.

Try to be consistent with your use of the spray apparatus. If you are clear and confident about the distance from the arm that works best, pay enough attention to keep the nozzle in that general range while maintaining a natural delivery as you would use the product under normal personal use. Keep the nozzle aimed at the skin surface, and avoid orienting the containers in

any ways that you determine, as you proceed with the trial, to interfere with delivery of the repellent to the skin surface.

Now move onto the **Spray Sampling** exercise described in the next section for the spray pump. After completing that exercise, you will return to the instructions above that you have just carried out and conduct the procedure for the lower legs, and then conduct Spray Sampling for the legs. Next repeat all of the above with the aerosol."

### 10.3.3. Spray Sampling

**Spray Sampling** is the procedure by which the spray is subsampled with patch dosimeters. Dosimeters of known surface area will be placed on subject lower arms. These dosimeters will intercept a portion of the spray applied to the arm. Be weighing dosimetry patches before and after treatment, the mass of the intercepted material can be calculated. The spray delivery systems will also be weighed before and after each application.

Spray sampling will be conducted according to the following procedure.

"Please read along with the Study Director as he reads aloud the following description of the procedures you will employ in spray sampling. Please be sure to ask questions at any point.

This procedure is very similar to what you have just performed. The main difference is that for spray sampling, a technician will place four narrow rings of plastic-backed gauze around each of your forearms. The rings are about one-half-inch (1.5 cm) wide. Each of these "gauze bracelets" will be centered on each of the four positions on the arm at which we initially measured the circumference. These positions may be marked on the skin with small but visible dot using a temporary marker.

The function of the "gauze bracelets" is to capture some of the spray that would otherwise reach your arm as you apply the test products. It is important that you do not alter the way in which you apply the materials in any intentional or substantial way from what you have already determined is your best procedure. The

technician will review your results from your previous applications with you to assist you in repeating your general procedure (distance of nozzle to skin, number of spray pumps or aerosol sweeps) as you apply the materials to one of your arms with the bracelets in place.

The gauze bracelets are narrow in order to minimize the extent to which your sensation of receiving the spray on the arm is changed. Do your best to proceed as if the sensation is not changed. In other words, attempt to avoid spraying additional material onto areas under the bracelets where the sensation of test material on the skin will be different or absent. Do not attempt to spray additional material directly onto a bracelet unless it is within an area that needs additional treatment. Again, attempt to repeat the procedure that you have already developed, and apply the materials "as if the bracelets were not there."

Put a new latex glove on each hand. Spray material onto one arm only. The technician will tell you to which arm to apply spray. You and the technician will collect the same data as previously.

After you have completed spraying, keep both arms from making contact with any surface. All bracelets will be removed by a technician and taken for weighing.

Discard your gloves, and wash both arms with cleanser and dry them thoroughly with a towel.

Repeat these procedures until you have made at total of three spray samples for the first arm, and three more for the second arm. Be sure to discard your gloves, and wash both arms with cleanser and dry them thoroughly with a towel, including after the last application."

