# 10.3.4. Lotion sampling

The amount of lotion applied to limbs will be quantified in a series of three applications analogous to the Spray Sampling above. However, dosimeters are not required, nor are the

extensive practice sessions. The amount applied is the weight difference in the dispensing tube before and after application.

The instructions are as follows:

"Put a new latex glove on each hand. You will apply lotion to one arm only. The technician will tell you to which arm to apply. You will begin with an amount that you suppose is about one half of what you will need to achieve thorough and uniform coverage. After spreading that around the lower part of your arm, you will apply more as needed to the area closer to your elbow. Begin by gently squeezing lotion from a tube with the cap open directly onto the horizontally-held surface of the opposite arm. Hand the tube to the technician. Using the tips of the index and middle fingers, spread the lotion as evenly as possible on all surfaces of the lower arm. Do not spread it onto the hand or beyond the marking on your wrist. If you have sufficient lotion left to spread it evenly and thoroughly toward the elbow, continue in the direction. Do note spread it beyond the elbow or past beyond the marking near the elbow. If you need more lotion to achieve thorough and even coverage, make sure you have wiped all repellent from your fingertips onto the skin and ask the technician to hand you the tube. Apply as much additional as you think you need, as before, but to complete the coverage. If you decide that you have applied more repellent that you would normally use to achieve thorough and even coverage, immediately have the technician wash and dry the treated arm so that none of the repellent you have applied is visible on close inspection, and begin again. Likewise, be careful to avoid dropping any lotion off of the arm, and if this happens, begin again as you would if you applied too much.

After you have completed an application successfully, the technician wash and dry the treated arm so that none of the repellent you have applied is visible on close inspection, and reweigh the tube. You will continue until you have completed three successful applications. Then you will repeat the entire procedure above, but with the lower leg."

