# 10.3.5 Equipment Used to Assess the Dosimetry Variable:

Passive dosimeters are 1.5 cm wide strips of 3M Brand NexcareTM HoldfastTM self-adhesive roll gauze attached to the adhesive side of 1.5 cm wide strips of 3M Brand clear packaging tape. The tape will retard test materials from passing from the dosimeter to the subjects' skin. The tape strip length will match the circumference of a given region of a subject's arm. The gauze strip will be 1.5 cm longer than the tape, in order to permit a 1.5 cm overlap onto the self-adhesive gauze bracelet, thus securing the dosimeter in place.

On the non-adhesive side tape strip (the inner surface of the dosimetry bracelet) the following notations will be made before they are used.

- a) Subject number
- b) L (for left placement) or R (for right arm placement)
- c) Position letter: a (wrist), b (next proximal), c (next proximal), d (elbow)
- c) T (for treatment) or C (for control)
- d) Replicate number (1, 2 or 3)

There will be eight bracelets per replicate. Each arm and leg will be treated three times. Each subject will therefore have a total of forty-eight custom bracelets made and labeled in advance.

Bracelets will be weighed before and after treatment on a traceably calibrated Sartorius H51 balance (measurement increment 0.0001 g, 30 g capacity). Test material containers (pump spray and aerosol) will be weighed before and after dispensing on a traceably calibrated Sartorius GC 2502 (measurement increment 0.001 g, 500 g capacity).

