# 11.3.1 Dosimetry:

Dosage will be calculated per square centimeter of skin. The amount of test material delivered to each dosimeter in each trial will be calculated as:

weight after application – weight before application

The **total captured** by all treated dosimeters per trial will be calculated by adding the mass changes in all four dosimeters together, and then subtracting or adding, respectively, any total gain of loss of weight in the paired control dosimeters.

The **proportion covered** of the total limb surface area by the dosimeters is:

Surface area of a set of 4 dosimeters
Surface area of the limb

The estimated **dosage per trial** is: **Total captured** x 1/**proportion covered** 

The specific gravity of each test material will be measured and used to convert the dosage weight data to volumes for preparing individual subject doses volumetrically for dispensing from the tuberculin syringes.

Subject means and standard deviations will be calculated for all measures of dosimeter weight changes as well as application behaviors (distance from nozzle to skin, duration of application, number of sweeps/pumps). Lotion, pump spray and aerosol statistics will be calculated separately and then compared with nonparametric tests for two- and three- sample independent cases (Wilcoxon match-pairs signed-rank and Kruskal-Wallis tests, respectively).

We will statistically assess the strength of any individual subject differences in application behavior and dosing in interaction with the three test materials using Friedman two-way analysis of variance subject dose means for each test material. We will use subject dose means for each test material to calculate dosing grand means (± SD) for each test material. Those means, expressed as repellent weight per unit skin surface area, will be used to determine individual subject doses in the field repellency test.

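### The four spray bracelets appear to include both limb ends yet count equally, so the end rings carry about 50% of the dose weight for about 33% of the limb length

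*Combined protocol and SAP*

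**What the plan says.** Section 10.3.1 computes limb area from the mean of four equally spaced circumferences, two outer and two inner, times the treated length. Site positions are recorded as distances from "the distal margin of the site of the most distal circumference site (i.e., at wrist or ankle"). Section 10.3.3 has each gauze bracelet "centered on each of the four positions on the arm at which we initially measured the circumference"; the rings are 1.5 cm wide. Section 10.3.5 labels them "Position letter: a (wrist), b (next proximal), c (next proximal), d (elbow").

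Section 11.3.1 obtains the captured mass by "adding the mass changes in all four dosimeters together", corrects for the control bracelets, and divides by the ratio of four-ring area to limb area. No position weights appear. The mean of the subject means, per unit skin area, then sets every field dose of that product.

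Two other records are planned: "Subject means and standard deviations will be calculated for all measures of dosimeter weight changes" (11.3.1), and "The spray delivery systems will also be weighed before and after each application" (10.3.3). Neither enters the dose formula. For lotion, no bracelets are used: "The amount applied is the weight difference in the dispensing tube before and after application" (10.3.4).

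**The concern.** A set of evenly spaced sites that includes both ends of a length does not sample that length evenly. Each end site has limb on one side only, so it stands for half as much length as an inner site. If all four count the same, the average leans towards what happens at the ends.

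The ends are also where deposit could plausibly differ. Section 10.3.2 has aerosol subjects sweep from wrist to elbow and back, so starts, stops and reversals fall near the end rings. If a ring is centred exactly on the end mark, half of its 1.5 cm width lies outside the measured length. The coverage standard in 10.3.2 asks for "a continuous and complete layer of test material", which does not require equal thickness.

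Section 6.1.4 makes finding the dose a principal aim, and section 5.2 carries the same dosimetry data into the tick study. Since every subject on a product gets the same rate, the stake is not fairness between subjects. It is whether the field dose is the amount users typically apply, as 5.1 intends. An underdose would probably be conservative for a protection claim; an overdose would not.

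**Working it through.** The plan states no ring weights, so they are derived from its formulas.

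**Weight of each ring.** Let C be the four circumferences, L the length and m the four corrected masses.
- Limb area = mean(C) × L (10.3.1). Dosimeter area = 1.5 × sum(C) (10.3.5, ignoring the small gauze overlap).
- Dose = sum(m) × limb area / dosimeter area = L × mean(m/1.5).
- The circumferences cancel, so each ring has weight exactly 1/4 on mass per cm of length.

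**Length each ring represents** (nearest-site shares).
- Sites at 0, L/3, 2L/3 and L represent 1/6, 1/3, 1/3 and 1/6.
- End rings: weight 2 × 1/4 = 50%; length 2 × 1/6 = 33.3%; ratio 0.50/0.333 = 1.5.
- Relative to the length represented, an end ring counts (1/4)/(1/6) = 1.5 and an inner ring (1/4)/(1/3) = 0.75, a factor of two.
- With end sites inset 0.75 cm, so that each ring lies wholly on the limb, the end share is 36–38% (assumed L of 22–40 cm).
- Sites at interior fifths give 60%. Sites at L/8, 3L/8, 5L/8 and 7L/8 give 50%, which matches the weight.

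**Effect on the derived rate.** All spray profiles below are assumptions.

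*Ratio model:* density r at the ends, 1 at the inner marks and between them, linear in the outer thirds. Derived rate with end sites = (r + 1)/2; true rate = (r + 2)/3; derived rate with midpoint sites = (1.375 + 0.625r)/2.

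| r | End sites / true | Midpoint sites / true |
|---|---|---|
| 0.5 | 0.750/0.833 = 90.0% | 101.3% |
| 0.8 | 0.900/0.933 = 96.4% | 100.5% |
| 1.0 | 100% | 100% |
| 1.2 | 1.100/1.067 = 103.1% | 99.6% |
| 1.5 | 1.250/1.167 = 107.1% | 99.1% |

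*Sharp cut-off at the marks:* each end ring catches half its width, so (2 × 1.5 + 2 × 0.75)/6 = 75%. Midpoint sites give 100%.

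*Soft edge with overshoot o:* deposit(x) = Φ((x + o)/s) − Φ((x − L − o)/s), with L = 25 and 38 cm and s = 1.5, 2.5 and 4 cm.

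| o (cm) | Sites at the ends | Ends inset 0.75 cm | Midpoints |
|---|---|---|---|
| 0 | 77–85% | 85–89% | 102–104% |
| 2 | 88–96% | 91–99% | 100–102% |
| 3 | 91–99% | 94–100% | 100–101% |
| 5 | 96–100% | 97–100% | 100–101% |

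*Extra deposit where sweeps turn:* a Gaussian excess (SD 2 cm) at each sweep end, added to the soft edge with o = 0 or 2 cm. At heights of 25%, 50% and 100% of the middle level, end sites give 87–102%, 95–108% and 108–121%; midpoint sites give 99–102%, 98–101% and 93–99%.

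Midpoint sites were closer to the true rate than end sites in every ratio (r other than 1) and soft-edge run, and in 35 of the 36 turn-round runs.

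**The case against.** The strongest reply is that the end placement is inferred. Section 10.3.1 calls the outer sites peripheral, the bracelet letters are labels rather than coordinates, and the lotion instructions mention a marking near the elbow. A modest inset nearly removes the error in the ratio model: on a 25 cm forearm with r = 0.8 or 1.2, a 2 cm inset gives 99.0% or 100.9% of the true rate, and 3 cm gives 100.3% or 99.8%. That is fair as arithmetic. But 3 cm on 25 cm is almost exactly the midpoint layout (25/8 = 3.1 cm), which the protocol does not specify, and its only explicit statement about the distal site puts it at the wrist or ankle.

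The second reply is that unequal weighting is not itself bias. This stands. Uniform deposit carried past the marks gives 100%, the instructions push towards complete coverage, and nothing in the documents shows an end-to-middle gradient.

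The third is that the consequence is small. If protection time were proportional to dose (an assumption), 3.6% of the roughly 180 minutes cited in 9.1.3 is about 6.5 minutes, against a projected interval of 155–205 minutes at N = 10 and 15-minute readings. This also stands, and supports a low severity.

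The last is that position labels, recorded distances and container weights would let an end effect be seen. They would, but the dose rule uses none of them.

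**Conclusion.** The concern holds, at minor severity. The 50% against 33% follows from the plan's own formulas once the end sites are read as lying at the limb ends, which is the most natural reading but is not spelled out. Whether this biases the pump and aerosol rates depends on a spray profile that the documents do not give. Under moderate assumed gradients (r = 0.8–1.2) the error is about −4% to +3%. The assumed extremes run from 75% of the true rate (sharp cut-off exactly at the marks) to 121% (deposit raised by 100% at the turns). Direction is unknown. Lotion rates are unaffected, and the effect on complete protection time cannot be quantified because no dose–protection relation is given.

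**What to change.** Before dosimetry, reword 10.3.1, 10.3.3 and 10.3.5. Divide the treated length into four equal segments, then measure each circumference and centre each bracelet at the segment midpoints: 1/8, 3/8, 5/8 and 7/8 of the length, with a the most distal and d the most proximal. Keep the equal weighting in 11.3.1, since each ring then stands for one quarter of the length. Use the same sites for every limb-area calculation, lotion included, so that area means the same in dosimetry and field dosing.

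As a check, tabulate deposit per cm² by position a–d before field doses are set. The dose rule itself does not change.

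The cost is wording only: the numbers of bracelets, measurements and weighings stay the same, and the check uses weights already recorded by position. The change reduces the error without abolishing it; over the profiles above, midpoint sites still err by −7% to +4%. Moving the sites is better than reweighting end-site data by 1/6, 1/3, 1/3, 1/6 afterwards. Under the sharp cut-off, reweighting recovers only (1/3) × 0.5 + (2/3) × 1 = 83%, because half of each end ring lay outside the sprayed length.
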